Corneal confocal microscopy	(Antra)									-
мегозсору	Inferior								10	ourn(
	Systemic fatty acid level analysis									
Blood pin-prick test							j		5	University of Melbourne
			Re	tinopa	athy G	radin	g			
Retinal imaging	Right								- 10	Univ
	Left									
Recheck eligibility										
		ı		Rand	omisa	tion				
Randomisation	-									
Dispense study supplements	-								5	
Collection of unused supplements	-		D.		N	Г				
			Perip	neral	Nerve	Funct	lion			
MDNS									10	3J
CSP									15	s Hospital
QSART									15	
Nerve Excitability									15	cent,
Nerve Conduction									15	St Vincent'
Systemic Health] []	
Fasting blood test									10	

5. Response measures and summary of data collection methods

5.1. Efficacy measures:

5.1.1. Primary efficacy measures:

PrimaryOutcome:

Central Corneal Nerve Fibre Length (CNFL) (measured in mm/mm² using a Heidelberg Rostock Tomographer III with corneal module,

quantified using a fully-automated method (ACCMetrics))

Timepoint: Change in CNFL from Day 1 at Days 90 +/- 14, 180 +/- 24

5.1.2. Secondary efficacy measures:

SecondaryOutcome:
Central Corneal Nerve Fibre Density (CNFD) (measured in mm/mm²
using a Heidelberg Rostock Tomographer III with corneal module,

using a Heidelberg Rostock Tomographer III with corneal module, quantified using a fully-automated method (ACCMetrics))

Timepoint: Change in CNFD from Day 1 at 90 +/- 14, 180 +/- 24

Secondary Central Corneal Nerve Branch Density (CNBD) (measured in

Outcome: mm/mm² using a Heidelberg Rostock Tomographer III with corneal

module, quantified using a fully-automated method (ACCMetrics))

Timepoint: Change in CNBD from Day 1 at Days 90 +/- 14, 180 +/- 24

SecondaryOutcome:

Central corneal thresholds to a room-temperature air stimulus (measured in mBar using a non-contact corneal aesthesiometer)

Timepoint: Change from Day 1 at Days 90 +/- 14, 180 +/- 24

Secondary Central corneal thresholds to a cooled stimulus (measured in mBar

Outcome: using a non-contact corneal aesthesiometer)

Timepoint: Change from Day 1 at Days 90 +/- 14, 180 +/- 24

Secondary Change in health state (index score and visual analogue score as

Outcome: measured using the EQ-5D-5L questionnaire). Timepoint: Change from Day 1 at Day 90 +/- 14, 180 +/- 24

Secondary Michigan Neuropathy Screening Score (MNSI) composite score

Outcome:

Timepoint: Change from Day 1 at Day 180 +/- 24

Secondary Michigan Diabetic Neuropathy Score (MDNS) (measured through

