Outcome: clinical examination)

Timepoint: Change from Day 1 at Day 180 +/- 24

Secondary Routine nerve conduction studies (NCS) –sural sensory amplitude

Outcome: (measured using Dantec Keypoint G4 Workstation)

Timepoint: Change from Day 1 at Day 180 +/- 24

Secondary Routine nerve conduction studies (NCS) – peroneal motor velocity

Outcome: (measured using Dantec Keypoint G4 Workstation)

Timepoint: Change from Day 1 at Day 180 +/- 24

Routine nerve conduction studies (NCS) - tibial motor minimum F-**Secondary** Outcome: wave latency (measured using Dantec Keypoint G4 Workstation)

Timepoint: Change from Day 1 at Day 180 +/- 24

Nerve excitability profile: Depolarising threshold electrotonus (TEd) **Secondary** Outcome: (peak), TEd (90-100 ms), hyperpolarising threshold electrotonus

> (Teh) (90-100 ms), TEd (10-20 ms), superexcitability, subexcitability, resting current-voltage (I/V) slope, strength duration time constant

(measured with QTRAC software using TROND protocol)

Timepoint: Change from Day 1 at Day 180 +/- 24

Secondary Quantitative sudomotor axonal reflex testing (QSART), measured at

Outcome: the foot in sweat volume in nL using the QSWEAT system.

Timepoint: Change from Day 1 at Day 180 +/- 24

Secondary Cutaneous silent period testing: upper and lower limb (measuring

Outcome: silent period onset latency and duration) Timepoint: Change from Day 1 at Day 180 +/- 24

5.2. Safety measures:

Safety Outcome: Adverse events (AEs) reported

Timepoint: Change from Day 1 at Days 30 +/- 14, 90 +/- 14, 180 +/- 24

Safety Outcome: Change in habitual visual acuity measured using a standard eye chart

Timepoint: Change from Day 1 at Days 30 +/- 14, 90 +/- 14, 180 +/- 24

Change in intraocular pressure (IOP) measured using a Goldmann **Safety Outcome:**

tonometer

Timepoint: Change from Day 1 at Day 180 +/- 24

Safety Outcome: Diabetic retinopathy graded using the Wisconsin Scale grading system

Change from Day 1 at Day 180 +/- 24

Secondary Blood samples (measuring fasting glucose, fasting lipid profile [LDL, **Outcome:**

HDL, total cholesterol, triglycerides], FBC, ESR, CRP, Vitamin B-12,

Folate, TSH, UEC, HbA1c, liver function, electrolytes)

Timepoint: Change from Day 1 at Day 180 +/- 24

5.3. Compliance measures:

Compliance Total omega-3 status obtained from blood finger spot test (Waite

Outcome: Lipid Analytical Services)

Change from Day 1 at Day 180 +/- 24 Timepoint:

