11.2.1 Michigan Diabetic Neuropathy Score (MDNS) and routine nerve conduction studies (NCS)

[figure not shown]
The first part of the MDNS is a clinical examination, which is then followed by routine nerve conduction studies. Vibratory threshold perception is assessed with a 128 Hz tuning-fork. Light touch is assessed with a 10g monofilament applied to the dorsum of the great toe. Deep tendon reflexes and muscle strength testing formed the remainder of the clinical examination score. Nerve conduction studies are then performed using an electromyographic (EMG) device (Dantec Keypoint G4 Workstation), examining the right upper and lower extremities, and included median, peroneal and tibial motor studies, and sural, median and ulnar sensory studies. Abnormal parameters are defined as amplitudes, conduction velocities or latencies that exceeded two standard deviations from the normal values of our laboratory. Testing is performed with a target temperature of 32 degrees Celsius in the upper extremity and 30 degrees Celsius in the lower extremity. Participants are given a composite score (from class 0 to 3) based on their clinical examination and nerve conduction study results.

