To evaluate the effects of a six-month supplementation period with oral long-chain omega-3 PUFA supplements on peripheral nerve health in individuals with type-1 diabetes, as measured by the change from baseline in central corneal nerve fibre length (CNFL) at day 180.

Aim 2

To evaluate the effects of a six-month supplementation period with oral long-chain omega-3 PUFA supplements in individuals with type-1 diabetes on the change from baseline at day 180 for:

Key secondary outcomes:

Other corneal nerve structure and function parameters

[2 main variables for corneal nerve structure: central corneal nerve branch density (CNBD) and central corneal nerve fibre density (CNFD)

2 main variables for corneal nerve function: central corneal sensitivity thresholds to room and cooled temperatures]

Secondary outcomes:

- Patient-reported quality of life

[2 main variables: EQ-5D-5L VAS and Index]

- Small nerve fibre function

[6 main variables: CSP onset latency and duration in the upper limb, CSP onset latency and duration in the lower limb, QSART sweat volume and latency in the foot]

- Large nerve fibre function

[2 symptom/clinical sign composite score variables: MNSI and MDNS (clinical examination) scores]

[3 main neurophysiology variables: sural SNAP amplitude, peroneal motor conduction velocity and tibial minimum F-wave]

- Median nerve excitability

[8 main variables: Depolarising threshold electrotonus (TEd) (peak), TEd (90-100 ms), hyperpolarising threshold electrotonus (Teh) (90-100 ms), TEd (10-20 ms), superexcitability, subexcitability, resting current–voltage (I/V) slope, strength duration time constant]

Aim 3

To evaluate the safety of a six-month supplementation period with oral long-chain omega-3 PUFAs in individuals with type-1 diabetes, by evaluating the incidence of adverse events, change in habitual distance visual acuity, change in intraocular pressure, change in diabetic retinopathy grading, and change in blood pathology parameters from baseline at day 180.

3. Analysis sets/Populations

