R	QSART sweat latency - measured at the foot	s	<qsart_foot_lat></qsart_foot_lat>
	Small fibre function: exploratory		
D	QSART neuropathy grading (neuropathy/ length-dependent)	0 = None 1 = Length-dependent SFN 2 = Non-length dependent SFN	<qsart_neuropathy></qsart_neuropathy>
R	QSART: forearm volume	uL	<qsart_forearm_vol></qsart_forearm_vol>
R	QSART: forearm latency	s	<qsart_forearm_lat></qsart_forearm_lat>
R	QSART: proximal leg volume	uL	<qsart_proxleg_vol></qsart_proxleg_vol>
R	QSART: proximal leg latency	S	<qsart_proxleg_lat></qsart_proxleg_lat>
R	QSART: distal leg volume	uL	<qsart_distleg_vol></qsart_distleg_vol>
R	QSART: distal leg latency	S	<qsart_distleg_lat></qsart_distleg_lat>
	Large fibre function: secondary		
R	Michigan Neuropathy Screening Instrument (MNSI) score	Range: 0 to 23	<mnsi_total></mnsi_total>
R	Michigan Diabetic Neuropathy Score (MDNS) composite score: clinical examination	4 Levels: 0 = Class 0 1 = Class 1 2 = Class 2	<mdns_clin_class></mdns_clin_class>

	Variable label	Unit	Variable in data set
		3 = Class 3	
R	Nerve conduction studies: Sural SNAP amplitude (Mid. lower leg-Lat. malleolus)	uV	<sensory_sural_amp></sensory_sural_amp>
R	Nerve conduction studies: Peroneal CMAP velocity (Bl. knee – ankle)	m/s	<motor_peroneal_vel></motor_peroneal_vel>
R	Nerve conduction studies: Tibial minimum F-wave latency (Ankle – Abd hal)	ms	<motor_tibial_fminlat></motor_tibial_fminlat>
	Large fibre function: exploratory		
R	Michigan Diabetic Neuropathy Score (MDNS) composite score: neurophysiology composite score (NCS)	4 Levels: 0 = Class 0 1 = Class 1 2 = Class 2 3 = Class 3	<mdns_neurophys_clas s></mdns_neurophys_clas
R	NCS: median motor latency (wrist-APB)	ms	<motor_median_lat1></motor_median_lat1>
R	NCS: median motor amplitude (wrist-APB)	mV	<motor_median_amp1></motor_median_amp1>
R	NCS: median motor latency (elbow- wrist)	ms	<motor_median_lat2></motor_median_lat2>
R	NCS: median motor amplitude (elbow-wrist)	mV	<motor_median_amp2></motor_median_amp2>
R	NCS: median motor velocity (elbow-wrist)	m/s	<motor_median_vel></motor_median_vel>
R	NCS: peroneal motor latency (ankle-EDB)	ms	<motor_peroneal_lat1></motor_peroneal_lat1>
R	NCS: peroneal motor amplitude (ankle-EDB)	mV	<motor_peroneal_amp1< td=""></motor_peroneal_amp1<>
R	NCS: peroneal motor latency (Bl. knee-Ankle)	ms	<motor_peroneal_lat2></motor_peroneal_lat2>
R	NCS: peroneal motor amplitude (Bl. knee-Ankle)	mV	<motor_peroneal_amp2></motor_peroneal_amp2>

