Michigan Diabetic Neuropathy Score (MDNS) composite score: clinical examination class	Categorical variables with 4 ordinal levels	1, 180	Ordered logistic regression model
Nerve conduction studies: Sural SNAP amplitude (Mid. lower leg-Lat. malleolus)		1, 180	Repeated measures model.
Nerve conduction studies: Peroneal CMAP velocity (Bl. knee – ankle)			
Nerve conduction studies: Tibial minimum F-wave latency (Ankle – Abd hal)			
Nerve excitability			
Median motor nerve excitability profile: TEd (10-20 ms)			Repeated measures model.
Median motor nerve excitability profile: TEd (peak)			
Median motor nerve excitability profile: TEd (90-100 ms)			
Median motor nerve excitability profile: TEh (90-100 ms)			
Median motor nerve excitability profile: Superexcitability		1, 180	
Median motor nerve excitability profile: Subexcitability			
Median motor nerve excitability profile: Resting I/V slope			
Median motor nerve excitability profile: strength duration time constant			
Safety			
Habitual visual acuity measured using a standard eye chart - Right eye		1, 30, 90, 180	Repeated measures model.
Habitual visual measured using a standard eye chart - Left eye		1, 30, 90, 180	
Intraocular pressure - Right eye		1, 180	Repeated measures model.
Intraocular pressure - Right eye		1, 180	

SAP version 1.4 30-06-2020 Page 29 of 40

Outcome	Distribution/Transformation	Days	Analysis model
Diabetic retinopathy grading - Worst eye retinopathy grading	Categorical variable with 4 ordinal levels	1, 180	Ordered logistic regression model
Diabetic retinopathy grading - Worst eye macular oedema grading	Categorical variable with 3 ordinal levels.		
Bloods: HbA1C (mmol/mol)		1, 180	Repeated measures model.
Bloods: cholesterol			
Bloods: HDL			
Bloods: LDL			
Bloods: folate			
Bloods: vitamin B-12			
Bloods: creatinine			
Compliance			
Omega-3 index		1, 180	Repeated measures model.
Omega-3: EPA concentration			
Omega-3: DHA concentration			
Omega-6 concentration			
Omega-9 concentration			
Omega-6:Omega-3 ratio			

SAP version 1.4 30-06-2020 Page 30 of 40

15. **Appendix** 4 LIST OF TABLES/FIGURES

Number	Title – analysis set
Table 1	Baseline participant characteristics (Intention-To-Treat sample)
Table 2	Central corneal nerve efficacy outcomes (Intention-To-Treat sample)
Table 3	Clinical neurophysiology outcomes (Intention-To-Treat sample), including secondary outcomes for small nerve fibre function and large nerve fibre function
Table 4	Compliance (Intention-To-Treat sample)

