Habitual distance visual acuity (LogMAR) - Right eye - Left eye								
Intraocular pressure (mmHg) - Right eye - Left eye								
Diabetic retinopathy in the worse eye, n (%) - None - Mild - Moderate - Severe - Proliferative								
Diabetic macular oedema in the worse eye, n (%) - None - Macular oedema - Clinically significant macular oedema								
Blood biochemistry								
HbAıC (mmol/mol)								
Cholesterol (mmol/L)								
HDL (mmol/L)								
LDL (mmol/L)								
Creatinine (µmol/L)								
Vitamin B12 (pmol/L)								
Folate (nmol/L)								

^{*} Mean and standard deviation unless stated otherwise.

[†] p-values are not adjusted for multiple testing.

Abbreviations: HbAıC, haemoglobin Aıc; HDL, high-density lipoproteins; LDL, low density lipoproteins.

Changes from the planned analysis in the Statistical Analysis Plan

- 1. A sensitivity analysis was performed for outcomes with substantial imbalance at baseline either in the mean (continuous outcomes) or geometric mean (log base e transformed outcomes) between groups. The imposed constraint of balance at baseline of the constrained longitudinal data analysis model was removed by adjusting the primary model for the interaction between baseline and treatment in addition to the factors already part of the longitudinal data analysis model.
- 2. We had intended to analyse categorical and binary variables using (ordinal) logistic regression analysis. However, this model could not be fitted due to the distribution of the data within and between groups. Instead, for categorical and binary variables, change from baseline at the study endpoint for each participant was categorised as negative change, positive change, or no change. Fisher's exact test was used to compare the proportions of participants between treatment groups. For MDNS scores, in changing from analysing this parameter as a continuous variable to a categorical variable, the class of neuropathy (class 0–3 as defined by the MDNS) was derived as the highest score from the clinical scoring or neurophysiology component.

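### The secondary MDNS result uses the higher of the clinical and neurophysiology classes instead of the pre-specified clinical examination; the stated reasons support a new test, not a new variable

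*Combined protocol and SAP*

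**What the plan says.** **Planned outcome.** Protocol section 5.1.2 lists the MDNS as a secondary outcome assessed by clinical examination. SAP section 2, Aim 2, agrees: "2 symptom/clinical sign composite score variables: MNSI and MDNS (clinical examination) scores". Neither place mentions a class.

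The SAP appendices are more specific:
- Appendix 1 lists "Michigan Diabetic Neuropathy Score (MDNS) composite score: clinical examination" among the secondary large-fibre variables, with classes 0 to 3. It lists the MDNS neurophysiology class as a separate variable under the exploratory large-fibre heading.
- Appendix 2 derives the clinical class and the electrophysiology class on separate rows. It defines no combination of the two.
- Appendix 3 assigns ordered logistic regression to the clinical examination class, described as "Categorical variables with 4 ordinal levels".

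The Table 3 shell in Appendix 4 also names only the clinical examination, but shows it as a number out of 46, with mean and standard deviation as the default summary.

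**Reported analysis.** Item 2 of the changes from the planned analysis says that the logistic models could not be fitted. Change was therefore sorted into negative, none or positive and compared by Fisher's exact test. For the MDNS, the item adds that in moving from a continuous to a categorical analysis the class "was derived as the highest score from the clinical scoring or neurophysiology component".

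**The concern.** Item 2 makes two changes to the MDNS analysis, and only one follows from the model failure. The test changes, and so does the outcome. A component that the SAP classed as exploratory can now decide a pre-specified secondary result, and the plan has no rule for combining the two.

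If only the combined class is reported, readers lack the result that was promised. Nerve conduction is also already represented among the secondary outcomes by sural amplitude, peroneal velocity and tibial F-wave latency. Bringing it into the MDNS makes the clinical result less distinct from those three.

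**Working it through.** The plan gives no figure on this point to reproduce. The check has two parts.

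**1. Do the stated reasons require a new variable?**

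- *The model could not be fitted.* The replacement needs only the sign of each participant's change. Appendix 2 gives a clinical class from 0 to 3 without nerve conduction, so the sign of its change is defined and Fisher's test applies. This reason supports the new test only.
- *The outcome moved from continuous to categorical.* This matches the Table 3 shell (out of 46). It conflicts with Appendix 3, where the outcome was already a four-level category. On either reading, the clinical-only class supplies the categories. The move does not explain why the neurophysiology component was added.

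**2. Can the two definitions give different answers?**

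Let C0 and C1 be the clinical class at baseline and Day 180, and N0 and N1 the neurophysiology class. Each takes values 0 to 3 (Appendix 1), so there are 4 × 4 × 4 × 4 = 256 patterns. I read item 2's highest score as the higher of the two classes.

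- Planned direction: sign of (C1 − C0)
- Reported direction: sign of (max(C1, N1) − max(C0, N0))

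| Clinical class | Patterns | Same direction | Becomes no change | Becomes a change | Opposite |
|---|---|---|---|---|---|
| Changes | 12 × 16 = 192 | 122 | 48 | – | 22 |
| Does not change | 4 × 16 = 64 | 36 | – | 28 | – |

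The direction differs in 48 + 28 + 22 = 98 of 256 patterns and is opposite in 22.

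The 48 can be checked by hand. A maximum of m arises from 2m + 1 pairs, that is 1, 3, 5 and 7 pairs for m = 0 to 3. The maximum is therefore unchanged in 1 + 9 + 25 + 49 = 84 patterns. In 64 − 28 = 36 of these the clinical class is also unchanged, which leaves 84 − 36 = 48.

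If each component moves by at most one class, 10 × 10 = 100 patterns remain. The direction differs in 36 and is opposite in 6.

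Examples:
- Clinical 2 to 1, neurophysiology 2 to 2: clinical improvement, but the maximum is unchanged.
- Clinical 1 to 1, neurophysiology 2 to 1: no clinical change, but the maximum improves.
- Clinical 1 to 0, neurophysiology 1 to 2: clinical improvement, but the maximum worsens.

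These counts weight every pattern equally. They show that the endpoints are not interchangeable, not how often they disagreed in this trial.

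**The case against.** **A combined class has a basis in the protocol.** The MDNS part of protocol section 11.2.1 says "Participants are given a composite score (from class 0 to 3) based on their clinical examination and nerve conduction study results". Item 2 refers to classes as the MDNS defines them, and Appendix 2 defers to a scoring sheet that the documents do not reproduce. Highest-of-two may be the instrument's own rule. This stands as far as it goes: the documents do not show the rule to be an invention. But section 11.2.1 gives no highest-of-two rule, and a combined class is not the outcome listed in protocol 5.1.2 or in the SAP.

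**The stated reason is not false.** The Table 3 shell does treat the MDNS as numeric. This stands: the SAP is inconsistent with itself, and item 2 agrees with one part of it. The reason is incomplete, because it leaves the added component unexplained.

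**The stakes are low.** The change is openly listed. The MDNS is not a key secondary outcome, its p-value is not adjusted for multiplicity, and the SAP urges caution over such results. All of this stands and limits the weight of the point. Disclosure still does not supply the planned result.

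**Two stronger readings are tempting.**
- A reader might infer that the endpoint was redefined after its data had been modelled by arm, because item 2 blames the model failure on how the data fell within and across groups. That sentence concerns categorical and binary variables in general. The MDNS derivation is in a separate sentence, and nothing dates it.
- A reader might infer that the maximum hides any one-class clinical improvement when the baseline neurophysiology class is at least as high as the clinical one. That holds only if the neurophysiology class does not change. With it free to change, there are 24 such patterns, and 14 still register as improvement. The documents contain no MDNS data from which to estimate a share of hidden improvers.

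**Conclusion.** The point holds as a departure from the pre-specified secondary outcome that the stated reasons do not account for. The plan restricts the outcome to the clinical examination, and the reported analysis adds an exploratory component. The definitions can disagree on direction in 98 of 256 possible patterns, or 36 of 100 if each component moves by at most one class. This rests on reading item 2's score as a class, and the counts are not frequencies.

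The effect on the MDNS result cannot be judged. Supplementary Tables S1 to S10 contain no MDNS result, and it cannot be seen whether the clinical class was reported elsewhere. No direction of bias is claimed. The primary CNFL conclusion and the key secondary corneal outcomes do not depend on the MDNS.

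**What to change.** - Report change in the clinical examination class, with the same Fisher test, as the secondary MDNS result, if this has not already been done.
- Report the neurophysiology class as exploratory, as in Appendix 1.
- Keep the highest-of-two class only as a result labelled post hoc.
- In item 2, state why the neurophysiology component was added, and reconcile the continuous-to-categorical wording with Appendix 3 and the Table 3 shell.

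Both classes are variables in the SAP dataset, so no new data are needed. The cost is one extra table row and a few sentences. Sample size, power and alpha do not change.

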- Continuous repeated measures data collected at more than one visit will be analysed using a constrained longitudinal data analysis technique (Liang 2000). The outcome (dependent variable) will consist of the baseline and postbaseline values. The model will assume a common baseline mean across the two treatment arms due to random allocation. It will incorporate time point (study visit) as a categorical variable, thus it will not assume a specific trajectory over time. In addition to study visit, the model will include treatment as the main factor and the treatment by study visit interaction. The variancecovariance among the repeated measurements will be defined as unstructured. In the case of non-convergence, we will consider alternative structures (first-order autoregressive, Toeplitz, compound symmetry). Using this model, study participants with a missing baseline or a missing postbaseline value will be included in the analysis but study participants with no outcome values will be excluded. This model will yield unbiased results when the outcome data are Missing At Random. We will report the estimate and two-sided confidence interval of the absolute difference between two treatment groups in the change from baseline to 3 months and 6 months postbaseline (if applicable). Before fitting this model, the distribution of the outcome will be explored. In addition, we will examine if there are potential violations of underlying model assumptions (e.g. residuals). As a result, we may apply an appropriate transformation (e.g. log-transformation) before fitting the final model.
- Binary data will be analysed using a logistic regression model. We will report
 the estimate and two-sided confidence interval of the odds ratio between the
 two treatment groups.
- Categorical data will be analysed using an ordinal logistic regression model.
 We will report the estimate and two-sided confidence interval of the odds ratio between the treatment groups.

Details of which model will be used for each of the primary, key secondary, and secondary outcomes can be found in Appendix 3.

Compliance

See Table 4 in **Appendix 4**.

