- 3. Between-group comparisons of dry eye symptom scores using the exploratory outcome of Ocular Surface Disease Index (OSDI) (appendix 3) could not be performed using the prespecified repeated measures model due to the number of scores with the value of zero. For the OSDI outcome, comparison of change between the omega-3 PUFA and placebo groups was tested using the non-parametric Wilcoxon rank sum test. The estimate and 95% confidence intervals between-groups were obtained using the Hodges-Lehman non-parametric estimator.
- 4. Total omega-3 concentrations (%) are not additionally analysed as EPA and DHA concentrations have been reported.
- 5. Exploratory outcomes for indirect health care were not analysed.

[figure not shown]

Figure S1. CONSORT diagram. PUFA=polyunsaturated fatty acid. ^aOne participant in the omega-3 PUFA group completed the study but did not undergo procedures relating to small or large nerve fibre function in the limbs.

[figure not shown]

Figure S2. Axonal nerve excitability studies at baseline and endpoint (Intention-To-Treat sample). Threshold electrotonus at day 0 (dashed line) and day 180 (solid line) in (A) the omega-3 PUFA group and (B) the placebo group. *Asterisk indicates significant between-group difference for change in hyperpolarising threshold electrotonus at the 90-100ms interval (TEh 90-100 ms) during a -40% control threshold stimulus.

Table S1. Summary of concomitant systemic medications (Intention-To-Treat sample)

Medication category	Omega-3 PUFAs	Placebo
	(n=21)	(n=22)
None	5 [24%]	7 [32%]
At least one concomitant medication	16 [76%]	15 [68%]
Blood Products and Modifiers	1 [5%]	1 [5%]
Analgesics	2 [10%]	3 [14%]
Antibacterials	1 [5%]	1 [5%]
Anticonvulsants	0 [0%]	2 [9%]
Antidepressants	1 [5%]	3 [14%]
Antiparasitics	0 [0%]	1 [5%]
Blood Glucose Regulators	1 [5%]	0 [0%]
Cardiovascular agents	15 [71%]	13 [59%]
Contraceptives	2 [10%]	1 [5%]
Dermatological agents	1 [5%]	3 [59%]
Electrolytes/Minerals/Metals/ Vitamins	12 [57%]	6 [27%]
Vitamins	7 [33%]	5 [23%]
Electrolyte/Mineral Replacement	5 [24%]	1 [5%]
Gastrointestinal Agents	3 [14%]	0 [0%]
Genetic or Enzyme Disorder: Replacement, Modifiers, Treatment	1 [5%]	1 [5%]
Hormonal Agents, Stimulant/Replacement/ Modifying (Thyroid)	1 [5%]	2 [9%]
Immunological Agents	1 [5%]	1 [5%]
Inflammatory Bowel Disease Agents	0 [0%]	1 [5%]
Respiratory Tract/ Pulmonary Agents	2 [10%]	1 [5%]
Sleep Disorder Agents	1 [5%]	0 [0%]

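### Table S8: the placebo Day 180 spread in three depolarising threshold electrotonus windows points to one or a few extreme recordings, on which the estimates for two secondary outcomes heavily depend

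*Combined protocol and SAP*

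**What the plan says.** SAP Section 2 (Aim 2) and Appendix 3 name eight median nerve excitability variables as secondary outcomes. Two of them matter here: "Median motor nerve excitability profile: TEd (peak" and "Median motor nerve excitability profile: TEd (90-100 ms" (each label cut before its closing bracket). TEd 40-60 ms and S2 accommodation are exploratory. The results are in Table S8, and the curves in Figure S2, captioned "Threshold electrotonus at day 0 (dashed line) and day 180 (solid line) in (A) the omega-3 PUFA group and (B) the placebo group".

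For continuous repeated measures, SAP Section 6 (Statistical procedures) specifies a constrained longitudinal model. The distribution is explored first, and "we will examine if there are potential violations of underlying model assumptions (e.g. residuals" is the stated diagnostic step, after which a transformation may be applied. The SAP gives no rule for outlying values. SAP Section 9 records full source verification for the primary and key secondary outcomes, and otherwise for a random subset of at least 20% of the data. The list of changes from the planned analysis says nothing about individual excitability recordings.

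**The concern.** Placebo spread at Day 180 is ordinary early in the depolarising current and then becomes very large. With 18 recordings in that cell, one or two values can set both the mean and the SD. The printed differences and intervals for two named secondary outcomes may then describe very few traces rather than the arm. If Figure S2B plots group means, its late depolarising segment is shifted too.

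An extreme neurophysiology value did reach another table of the supplement. In Table S6, placebo Day 180 sural velocity is 70.91 (SD 99.31) after a baseline of 48.25 (7.50). With n = 18, one value of about 468 m/s would account for this and leave the other 17 averaging about 47.5. Excitability data lay outside the full source verification, so a query is reasonable.

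**Working it through.** **Inputs (Table S8).** Day 180 n: placebo 18, omega-3 16. Cells are mean (SD).

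| Window | Placebo baseline | Placebo Day 180 | Placebo change | Omega-3 Day 180 | SD ratio, Day 180 |
|---|---|---|---|---|---|
| TEd 10-20 | 67.99 (4.30) | 68.00 (4.71) | -0.74 (4.25) | 70.27 (4.71) | 1.0 |
| TEd peak | 67.58 (4.48) | 69.39 (9.02) | 1.37 (9.81) | 69.45 (4.69) | 1.9 |
| TEd 40-60 | 53.25 (7.51) | 55.32 (11.98) | 1.80 (14.30) | 51.76 (3.60) | 3.3 |
| TEd 90-100 | 44.12 (4.89) | 47.49 (13.85) | 4.34 (15.21) | 44.94 (3.92) | 3.5 |

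**Reproducing the printed results.** SE = interval width / 3.92.
- TEd peak, -2.43 (-7.24 to 2.39): SE 9.63/3.92 = 2.46, p = 0.32 as printed.
- TEd 90-100, -2.90 (-9.87 to 4.07): SE 13.94/3.92 = 3.56, p = 0.41 to 0.42 (printed 0.42).

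I rebuilt the two-visit model from the moments. Within-arm covariance = (baseline SD² + Day 180 SD² - change SD²)/2, assuming completers share the full-sample baseline SD. For TEd peak this is 2.60 (placebo) and 14.14 (omega-3).
- TEd peak: pooled slope 0.419. Paired baselines are 70.25 and 68.02 (Day 180 mean minus mean change). The baseline-adjusted difference is 0.06 - 0.419 × 2.23 = -0.88. Releasing the equal-baseline constraint adds (0.419 - 1) × (70.24 - 67.58) = -1.54, giving -2.42 against -2.43 printed. This row therefore appears to come from the baseline-imbalance model; its double-dagger mark is not defined in the footnotes.
- TEd 90-100: slope -0.143, constrained estimate -2.55 + 0.143 × 1.97 = -2.27, SE 3.75. The printed -2.90 (SE 3.56) is only approximately recovered.

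**How extreme must the values be?** For k equal extreme values and 18 - k others with SD s: 17·SD² = (17 - k)·s² + [k(18 - k)/18]·(x - m)². Taking s = 4.5:

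| Window | One: x / mean of rest | Two | Three |
|---|---|---|---|
| TEd peak | 101.0 / 67.5 | 91.3 / 66.7 | 86.9 / 65.9 |
| TEd 40-60 | 100.0 / 52.7 | 86.1 / 51.5 | 79.8 / 50.4 |
| TEd 90-100 | 100.2 / 44.4 | 83.7 / 43.0 | 76.2 / 41.7 |

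For s from 4.0 to 5.0 the single value is 99.9-102.0, 99.2-100.7 and 99.5-100.8. The ceiling for a single value, mean + SD × 17/√18, is 105.5, 103.3 and 103.0. In TEd 10-20 it is 86.9, so no recording there can be near 100.

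**One recording or several?**
- At Day 180 placebo S2 accommodation equals peak minus 90-100: 69.39 - 47.49 = 21.90. Its SD of 7.03 implies a correlation of (9.02² + 13.85² - 7.03²)/(2 × 9.02 × 13.85) = 0.90. The same recording or recordings are probably extreme in both windows.
- In the other three arm-visit cells TEd peak lies 0.28 to 0.82 below TEd 10-20; in placebo at Day 180 it lies 1.39 above. Over 18 recordings the excess is 18 × 1.67 = 30 to 18 × 2.21 = 40. One value near 100 supplies about 33; two at about 91 would supply about 49.
- With one extreme value, the rest average close to the full placebo baseline means in all three windows. Against the paired baseline for TEd 90-100 (47.49 - 4.34 = 43.15), two values fit at least as well.

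**Removing one value of 100 (17 left).**
- TEd peak: placebo mean (18 × 69.39 - 100)/17 = 67.59, SD 4.94. With that person's unknown baseline between 61 and 68, the unconstrained estimate is about 0 to -0.6 and its SE about 1.1 to 1.8, so the printed 2.46 is about 1.4 to 2.2 times larger. The factor passes 2 only for a baseline of about 62 or less.
- TEd 90-100: placebo mean 44.40, SD 4.62. The raw Day 180 difference goes from -2.55 to +0.54. With a baseline between 36 and 44, the constrained estimate is about -0.5 to +1.0 and its SE 1.24 to 1.56, so the printed 3.56 is 2.3 to 2.9 times larger.
- TEd 40-60: the raw Day 180 difference goes from -3.56 to -0.93.

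**The case against.** A reader might infer that the data contain exactly one recording stuck at a 100% tracking ceiling. The documents do not support that. Only means and SDs are published, two or three less extreme recordings also reproduce them, and neither protocol Section 11.2.4 nor the SAP mentions saturation or a 100% limit.

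A single Day 180 recording also leaves some things unexplained. Placebo baseline TEd 40-60 already has SD 7.51, against 2.86 in the omega-3 arm. The printed placebo S2 change (0.24) differs from 1.37 - 4.34 = -2.97, and baseline S2 (21.62) differs from 67.58 - 44.12 = 23.46. Applying the one-value solution to the changes gives +38.4 (peak) and +63.0 (90-100), or about -24.7 in S2. Taking that out leaves the other 17 S2 changes with SD about 8.3, against 2.61 in the omega-3 arm.

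A second tempting inference is that the SAP was breached. It was not shown to be: the SAP plans a look at distributions and residuals but sets no exclusion rule, nothing shows that the look was omitted, and keeping every recording suits an intention-to-treat analysis.

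Finally, the consequence is limited. The printed p-values for the three windows are 0.32, 0.25 and 0.42. They are unadjusted, and SAP Section 7.1.1 asks for caution in reading such results. The primary and key secondary outcomes are untouched.

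All of this stands. It does not remove the anomaly: under any of the three counts the extreme values lie far from the rest.

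**Conclusion.** The concern holds as a data query with a material effect on two secondary estimates. One, or possibly two or three, placebo Day 180 recordings appear extreme from the TEd peak onwards. The balance of evidence favours one value near 100, without proving the number or the cause.

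If it is one such value, most of the printed TEd peak difference and essentially all of the TEd 90-100 difference come from it, and the 90-100 ms placebo mean is about 3 points too high (47.49 against 44.40). A doubling of the standard error or more is supported for TEd 90-100, but not securely for TEd peak. After removal both estimates lie within about one SE of zero, so the null reading does not change.

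These sizes assume a single value of 100, an ordinary SD for the other 17, completers with the full-sample baseline SD, and the baseline ranges shown. Confidence is moderate.

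**What to change.** Check the extreme placebo TEd recordings against the raw QTRAC traces: Day 180 for peak, 40-60 and 90-100 ms, and baseline for 40-60 ms.

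- If a trace is a recording failure, set the affected windows and the derived S2 accommodation to missing, refit, and correct Table S8 and Figure S2B.
- If it is a valid recording, keep it and report these outcomes with and without it, or with a robust estimate.

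In either case, disclose the step in the list of changes from the planned analysis. The cost is one source check and a refit of three or four models, with no new data. The downside is a small post hoc sensitivity analysis, which should be labelled as such.
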